12.3 Publication of study protocol and results

The key design elements of this protocol will be posted in a publicly accessible database such as clinicaltrials.gov. In addition, upon study completion and finalization of the study report the results of this trial will be either submitted for publication and/or posted in a publicly accessible database of clinical trial results.

12.4 Quality Control and Quality Assurance

Novartis maintains a robust Quality Management (QM) system that includes all activities involved in quality assurance and quality control, including the assignment of roles and responsibilities, the reporting of results, and the documentation of actions and escalation of issues identified during the review of quality metrics, incidents, audits and inspections.

Audits of investigator sites, vendors, and Novartis systems are performed or overseen by Novartis Pharma Auditing and Compliance Quality Assurance (or CRO working on behalf of Novartis), a group independent from those involved in conducting, monitoring or performing quality control of the clinical trial. The clinical audit process uses a knowledge/risk based approach.

Audits are conducted to assess GCP compliance with global and local regulatory requirements, protocols and internal SOPs, and are performed according to written Novartis processes.

13 Protocol adherence

This protocol defines the study objectives, the study procedures and the data to be collected on study participants. Additional assessments required to ensure safety of subjects should be administered as deemed necessary on a case by case basis. Under no circumstances is an investigator allowed to collect additional data or conduct any additional procedures for any research related purpose involving any investigational drugs under the protocol.

Investigators ascertain they will apply due diligence to avoid protocol deviations. If an investigator feels a protocol deviation would improve the conduct of the study this must be considered a protocol amendment, and unless such an amendment is agreed upon by Novartis and approved by the IRB/IEC and health authorities, where required, it cannot be implemented.

1.1 Scope of document

The RAP documents contain detailed information to aid the production of Statistics & Programming input into the Clinical Study Report (CSR) for trial “**CLYS006X2201**”.

The Statistical analysis plan (SAP) describes the implementation of the statistical analysis planned in the protocol for the final analysis, as well as the outputs planned for the interim analyses.

1.2 Study reference documentation

Commercially Confidential Information

1.3 Study objectives

1.3.1 Primary objective(s)

Primary objective(s)	Endpoints related to primary objective(s)

 To assess the efficacy of LYS006 versus placebo on facial inflammatory lesion counts in patients with moderate to severe inflammatory acne 	
 Baseline-adjusted total inflammatory facial lesion count at Week 12

1.3.2 Secondary objective(s)

Secondary objective(s)	Endpoints related to secondary objective(s)

 To assess the safety and tolerability of LYS006 in patients with moderate to severe inflammatory acne 	
 Number and severity of AEs

1.3.3 Exploratory objective(s)

Exploratory objective(s)	Endpoints related to exploratory objective(s)
--------------------------	---

Commercially Confidential Information

Exploratory objective(s)

Endpoints related to exploratory objective(s)

Commercially Confidential Information

Exploratory objective(s)

Endpoints related to exploratory objective(s)

Commercially Confidential Information

1.4 Study design and treatment

This is a randomized, placebo-controlled, subject and investigator blinded, multicenter, non-confirmatory, parallel-group, proof-of-concept study in adult patients with moderate to severe facial inflammatory acne. After an initial screening period (up to 4 weeks), the study will be conducted over a treatment period of 12 weeks to evaluate the clinical efficacy of LYS006 versus placebo. Fifty-six (56) patients will be randomized in a 3:1:3 ratio to one of the following treatment groups:

- Group 1: LYS006 capsules, high dose CCI N=24
- Group 2: LYS006 capsules, low dose CCI N=8
- Group 3: LYS006 placebo CCI , N=24

Commercially Confidential Information

Exposure to placebo will be limited to a maximum of 12 weeks.

After treatment period completion, all patients will enter a post-treatment safety follow-up period of 4 weeks without study drug administration.

The maximum duration of study participation will be 20 weeks.

Commercially Confidential Information

2 First interpretable results (FIR)

Commercially Confidential Information

Commercially Confidential Information

Commercially Confidential Information

Commercially Confidential Information

Commercially Confidential Information

3 Interim analyses

Commercially Confidential Information

4 Statistical methods: Analysis sets

For all analysis sets, subjects will be analyzed according to the study treatment(s) received. This implies that for subjects for whom the actual treatment received does not match the randomized treatment, the treatment actually received will be used for the analysis.

The Safety analysis set will include all subjects that received at least one dose of study drug.

Commercially Confidential Information

The PD analysis set will include all subjects with available PD data, who received any study drug and with no protocol deviations with relevant impact on PD data.

The analysis sets and protocol deviation codes are related as follows:

Table 4-1 Protocol deviation codes and analysis sets

Category Deviation code	Text description of deviation	Data exclusion
Subjects are excluded from all (safety) analysis in case of these protocol deviations:		Exclude subject completely from all (safety) analysis sets
INCL01	Deviation from inclusion criterion 1 (Written informed consent must be obtained before any assessment is performed)	Yes

Commercially Confidential Information

Subjects are excluded from PD analysis in case of these protocol deviations:		Exclude subject from PD analysis set
INCL01	Deviation from inclusion criterion 1 (Written informed consent must be obtained before any assessment is performed)	Yes

Commercially Confidential Information

If updates to this table are needed, an amendment to the SAP needs to be implemented prior to DBL.

Commercially Confidential Information

Commercially Confidential Information

Commercially Confidential Information

6 Statistical methods for Efficacy/Pharmacodynamic (PD) parameters

All subjects within the PD analysis set will be included in the PD data analysis.

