6.3 Treatment assignment and randomization

Randomized treatment will be assigned to individual patients by way of a randomization number on Day 1. Randomization of patients will be carried out by Interactive Response Technology (IRT) system.

The randomization number is only used to identify which treatment the patients have been randomized to receive. The Subject number assigned to a patient at screening remains the unique identifier for the patient throughout the study. For information on subject numbering, please see 'Subject numbering' section in the SOM.

Commercially Confidential Information

The randomization numbers will be generated using the following procedure to ensure that treatment assignment is unbiased and concealed from patients and investigator staff. A subject randomization list will be produced by the Interactive Response Technology (IRT) provider using a validated system that automates the random assignment of subject numbers to randomization numbers. These randomization numbers are linked to the different treatment arms, which in turn are linked to medication numbers. A separate medication list will be produced by or under the responsibility of Novartis Drug Supply Management using a validated system that automates the random assignment of packs containing the investigational drug(s).

The randomization scheme for subjects will be reviewed and approved by a member of the Randomization Office.

Follow the details outlined in the SOM regarding the process and timing of treatment assignment and randomization of patients.

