11.1 Analysis sets

For all analysis sets, subjects will be analyzed according to the study treatment(s) received.

The following analysis sets will be used and will be derived prior to database lock. As required, additional analysis sets will be defined in the Statistical Analysis Plan (SAP).

Safety Analysis Set

The safety analysis set will include all subjects that received at least one dose of study drug.

Commercially Confidential Information

Pharmacodynamic (PD) Analysis Set

The PD analysis set will include all subjects with available PD data, who received any study drug and with no protocol deviations with relevant impact on PD data. Protocol deviations leading to exclusion from the PD analysis set will be added in the SAP.

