11.4.3 Handling of missing values/censoring/discontinuations

All patients with available data after baseline and until Week 12 will be included in the interim and in the primary analyses. If study drug is permanently discontinued before Week 12, data collected after permanent discontinuation will not be considered for the purpose of the primary analyses. The primary variable analysis model is known to give unbiased results under the assumption that missing data are at random (MAR), i.e. given observed data the missingness does not depend on unobserved data. In the event that many patients discontinue treatment, alternative estimands considering the effect of LYS006 versus placebo may also be investigated. Further details will be provided in the Statistical Analysis Plan (SAP).

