6.1 Primary objectives

The primary aim of this study is to assess the efficacy of LYS006 versus placebo on inflammatory facial lesion counts in patients with moderate to severe inflammatory acne.

The primary analyses will be based on on-treatment data. Data recorded after a patient discontinues study treatment will not be included in the primary analyses. This corresponds to the aim of this proof of concept of assessing the effect of LYS006 when taken as planned versus placebo used alone.

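### The primary high-dose versus placebo contrast is grouped by treatment received, so it is not protected as a comparison of randomised arms

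*SAP*

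**What the plan says.** **Grouping.** Protocol 11.1 and SAP Section 4 carry the same sentence: "For all analysis sets, subjects will be analyzed according to the study treatment(s) received". The SAP spells out the consequence: for "subjects for whom the actual treatment received does not match the randomized treatment, the treatment actually received will be used for the analysis".

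**Set.** SAP Section 6, which contains the primary analysis, opens with "All subjects within the PD analysis set will be included in the PD data analysis". That set holds subjects with PD data "who received any study drug and with no protocol deviations with relevant impact on PD data" (Protocol 11.1; SAP Section 4 has the same definition). The only PD exclusion code visible in SAP Table 4-1 is INCL01, missing consent.

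**Who enters the primary analysis.** Protocol 11.4.3 and SAP 6.1.3.1 both say: "All patients with available data after baseline and until Week 12 will be included in the interim and in the primary analyses". Neither names the PD set or its deviation filter.

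**Aim.** SAP 6.1 gives the purpose as "assessing the effect of LYS006 when taken as planned versus placebo used alone". It offers this as the reason for leaving out data recorded after treatment is stopped.

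Safety and PD are the only visible analysis sets. The rest of Table 4-1 and the sensitivity analyses (Protocol 11.4.4, SAP 6.1.4) are redacted.

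**The concern.** Randomisation balances prognosis only between groups as allocated. A patient counted under whatever was actually taken, or left out because of something that happened after randomisation, is no longer placed by chance. The plan allows both for its primary contrast, by a stated rule rather than by silence.

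That contrast feeds the two proof-of-concept criteria (Protocol 11.4.2), with about 20 completers per main arm (Protocol 11.7), and informs whether a dose-ranging study starts (Protocol 1.4). At that size, one or two patients can matter if their handling is related to outcome and differs between arms.

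The unnamed set in Protocol 11.4.3 adds a smaller difficulty. From the protocol alone, one cannot tell whether a patient with post-baseline counts and a PD-relevant deviation is in or out.

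**Working it through.** **1. The rules side by side.** The treatment-received rule covers every analysis set, the primary model uses one of those sets, and so the rule governs the primary contrast. As worded it would also govern a redacted set. The aim in SAP 6.1 is linked to one device, dropping post-discontinuation data. That device works equally well with patients kept in their randomised arm.

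**2. Reproducing Table 11-1.** Stated inputs: criteria P(difference < 0) > 90% and P(difference < -0.288) > 50%; true effect 35%, or -0.431 on the log scale; 15 per arm at the interim and 20 at the final. The log-SD is not visible. With a flat prior and a normal approximation, success means an estimate below the smaller of -0.288 and -1.2816 × SE, where SE = SD × √(2/n).

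- Solving for 80% at the interim: SD = (0.431 - 0.288) / (0.8416 × √(2/15)) = 0.465.
- Interim at that SD: SE = 0.1698; null Φ(-0.288/0.1698) = 4.5%; power 80%.
- Success at either look (400,000 simulated trials): about 5% under the null and 87% at a 35% effect.

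One SD fits all four cells when the table is read as cumulative, which is how Protocol 11.7 describes it. The SD was fitted to the table, so this shows consistency, not confirmation. An SD of 0.40 gives 2.8% and 90% cumulatively and does not fit. An SD of 0.48 gives about 6% and 87%.

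**3. Reference case, final look alone, 20 per arm.** SE = 0.465 × √(2/20) = 0.1470. Since 1.2816 × 0.1470 = 0.188 is below 0.288, the 25% criterion binds, as it does in every case below. Null pass rate: Φ(-0.288/0.1470) = 2.5%. Power: Φ(0.143/0.1470) = 83.5%. Both are below the table's 5% and 87% because they count only the final look.

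**4. Exclusions.** Remove kH high-dose and kP placebo patients averaging d SD worse than their arm:

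shift = -kH·d·SD/(20 - kH) + kP·d·SD/(20 - kP); SE = SD·√(1/(20 - kH) + 1/(20 - kP)); null = Φ((-0.288 - shift)/SE).

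| kH, kP, d | Shift | SE | Null pass rate |
|---|---|---|---|
| 2, 0, 0 | 0 | 0.1511 | 2.8% |
| 1, 1, 1 | 0 | 0.1509 | 2.8% |
| 2, 2, 1 | 0 | 0.1550 | 3.2% |
| 2, 1, 1 | -0.0272 | 0.1529 | 4.4% |
| 2, 0, 1 | -0.0517 | 0.1511 | 5.9% |

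**5. Grouping.** One placebo patient receives a high-dose kit. As treated, the arms are 21 and 19, with SE = 0.465 × √(1/21 + 1/19) = 0.1472.

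- Mix-up unrelated to prognosis: 2.5%.
- Patient 1 SD better than average: shift = -(0.465/19 + 0.465/21) = -0.0466; null Φ((-0.288 + 0.0466)/0.1472) = 5.1%.
- As randomised: 2.5% in both cases.

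**6. Sensitivity to the SD.** At 0.48, the reference is 2.9%, two per arm 3.6%, two high-dose only 6.6%, and the prognosis-related kit error 5.7%.

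**7. Price of as-randomised grouping if kits are mixed up, true effect 35%.**

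- One high-dose patient given placebo: effect 0.431 × 0.95 = 0.409; power Φ((0.409 - 0.288)/0.1470) = 80%.
- One swap per arm: effect 0.431 × 0.90 = 0.388; power 75%.
- No error: 83%.

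**The case against.** The rule is declared and identical in both documents. The trial is non-confirmatory, and its criteria are guidance alongside other considerations. The aim can be read as supporting the rule: a placebo-randomised patient who took LYS006 did not have placebo alone, and one using a prohibited topical acne product, which Protocol 5.2 handles case by case, may not reflect study treatment alone. Wrong kits are unlikely because allocation is automated: "These randomization numbers are linked to the different treatment arms, which in turn are linked to medication numbers". SAP 6.1.3.1 sits under Section 6 and reads naturally as a data rule inside the PD set. The sets are derived before database lock, Table 4-1 changes only by SAP amendment, and Protocol 10.3 settles deviations and locks the database before treatment codes are released.

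Much of this stands. It makes the practical effect small and leaves Protocol 11.4.3 as the main place where a set must be named. The pre-lock sequence supports blinded exclusion decisions at the final analysis. It is not absolute: Protocol 6.4 lets programmers access treatment assignment for analysis, and Protocol 10.4 has the sponsor's team compare high dose with placebo at the first interim.

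What does not stand is that the aim requires the rule. An as-treated supportive run answers the question about treatment as taken, while the primary contrast keeps the randomised arms.

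A reader might infer that the filter removes poor responders, or that no as-randomised analysis exists. The documents support neither. The only visible exclusion code is consent, and the redacted text could hold further codes or such an analysis.

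**Conclusion.** The point holds in a limited form. By a stated rule, the primary contrast is grouped by treatment received in a deviation-filtered set, and no as-randomised primary population is visible. The on-treatment aim does not require this.

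The size is conditional. Neutral or balanced exclusions move the final-look null pass rate from 2.5% to between 2.8% and 3.2%. It reaches 5% to 6% only if errors or exclusions are both related to outcome and unequal between arms, and nothing documents any. These figures assume a log-SD of 0.465, which the visible text does not state, 20 per arm, a two-sample approximation to the repeated-measures model, and the final look alone. They should not be set against the cumulative 5% in Table 11-1.

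A reader might also infer that an as-randomised population would make the comparison free of selection. It would not: the on-treatment rule and the assumed dropout of about 20% remain. The change reduces selection without removing it.

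**What to change.** In Protocol 11.1 and 11.4.3, and SAP Sections 4 and 6:

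- Restrict the treatment-received rule to safety (and PK, if applicable).
- Name one primary efficacy set: randomised, consented patients who took at least one dose and have at least one on-treatment post-baseline count, analysed in the randomised arm. INCL01 stays as an exclusion, and the on-treatment data rule stays.
- State that the inclusion sentence in Protocol 11.4.3 and SAP 6.1.3.1 applies within that set.
- Keep the as-treated, deviation-filtered PD set as a supportive run.
- If an interim is held, fix the PD exclusion codes before its comparative results are seen.
- If a redacted section already gives an as-randomised analysis, cross-refer to it by name in SAP 6.1.3.

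The cost is a protocol amendment with the approvals in Protocol 13.1, a matching SAP edit, one extra model run, and the slight dilution in step 7 of the working if kits are mixed up. The supportive run would show the result without that dilution.

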6.1 Primary objectives

The primary aim of this study is to assess the efficacy of LYS006 versus placebo on inflammatory facial lesion counts in patients with moderate to severe inflammatory acne.

The primary analyses will be based on on-treatment data. Data recorded after a patient discontinues study treatment will not be included in the primary analyses. This corresponds to the aim of this proof of concept of assessing the effect of LYS006 when taken as planned versus placebo used alone.

6.1.1 Variables

The primary variable is the natural log transformed total inflammatory facial lesion counts (sum of papules, pustules, and nodules) at Week 12.

Baseline is defined as the Baseline (Visit 2) assessment.

6.1.2 Descriptive analyses

Total inflammatory facial lesion count will be listed by treatment group, subject and visit/time, and descriptive statistics will be provided, for raw, absolute change from baseline and percentage change from baseline, by treatment group and visit/time. Summary statistics will include mean (arithmetic and geometric), SD, CV (arithmetic and geometric), median,

minimum, maximum; geometric mean and its CV will only be provided for the raw values. A geometric mean will not be reported if the dataset includes zero values.

Graphical methods will be employed to show mean and individual (Spaghetti) plots over time.

Commercially Confidential Information

Note: Any plots that are reported separately by treatment (i.e., plots with one graph per page for each treatment), will use the same y-axis scale for each treatment.

6.1.3 Statistical model, assumptions and hypotheses

Data up to Week 12 will be included in a Bayesian mixed effect model for repeated measures (MMRM) for the comparison of LYS006 high dose group versus placebo group at 12 weeks, which is of primary interest. Data from the LYS006 low dose group will also be included in this primary model at the time of IA and later analyses, but will mainly be summarized as described in the descriptive analyses section above.

The natural log transformed inflammatory facial lesion count is expected to be approximately normally distributed. It will be analyzed using a Bayesian mixed effect model for repeated measures (MMRM) using Proc MCMC in SAS software ([Chen 2011](#)). Baseline adjustment will be implemented by including the log transformed baseline inflammatory facial lesion count in the model as a continuous covariate. The model will also include treatment group, visit, treatment group by visit interaction, log transformed baseline inflammatory facial lesion count

Commercially Confidential Information

as fixed effects. Non-informative priors will be utilized for the fixed effects and for the covariance coming from a normal distribution and an inverse Wishart distribution, respectively. An unstructured covariance will be assumed; other covariance structures will be investigated if there is a convergence issue. The log transformed baseline inflammatory facial lesion count will be centered and standardized prior to being included in the model.

Bayesian posterior probabilities will be used to assess the following proof-of-concept (PoC) criteria as a guidance for decision making ([Fisch et al 2015](#)), though other criteria may be taken into account:

Efficacy criteria (only for primary objective) at IA and at the final analysis:

- If there is at least 90% probability that the treatment effect of LYS006 at 12 weeks is better than placebo, i.e., $\text{Prob}(y_{\text{LYS006}} - y_{\text{placebo}} < 0) > 90\%$, and
- If there is at least 50% probability that the treatment effect at 12 weeks is at least 25% in favor of LYS006, i.e., $\text{Prob}(y_{\text{LYS006}} - y_{\text{placebo}} < -0.288) > 50\%$.

Where y is the log transformed facial inflammatory lesion count.

The posterior estimates of the treatment effect and the treatment difference (along with its 90% credible interval) at each post baseline visit (with Week 12 being of primary interest) will be provided. The results of the treatment effects will be presented as geometric means by back-transforming the estimates from the log-scale. The results of the treatment comparison to

placebo will be reported in terms of ratio of the geometric means by back-transforming the estimates from the log-scale.

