11.4 Analysis of the primary variable(s)

The primary aim of this study is to assess the efficacy of LYS006 versus placebo on inflammatory facial lesion counts in patients with moderate to severe inflammatory acne. Therefore, a statistical analysis will be performed on the log transformed inflammatory facial lesion count after 12 weeks. The primary analyses will be based on on-treatment data. Data recorded after a patient discontinues study treatment will not be included in the primary analyses. Commercially Confidential Information

11.4.1 **Primary Variable(s)**

The primary variable is the natural log transformed total inflammatory facial lesion counts (sum of papules, pustules, and nodules) at Week 12.

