6.1.3.1 Model checking procedures

All patients with available data after baseline and until Week 12 will be included in the interim and in the primary analyses. If study drug is permanently discontinued before Week 12, data collected after permanent discontinuation will not be considered for the purpose of the primary analyses. The primary variable analysis model is known to give unbiased results under the assumption that missing data are at random (MAR), i.e. given observed data the missingness does not depend on unobserved data. In the event that many patients discontinue treatment, alternative estimands considering the effect of LYS006 versus placebo may also be investigated.

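### Does the lack of a zero-count rule for the log-transformed primary endpoint bias the trial against a drug that clears patients?

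*SAP*

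**What the plan says.** Protocol 11.4.1 defines the endpoint: "The primary variable is the natural log transformed total inflammatory facial lesion counts (sum of papules, pustules, and nodules) at Week 12". SAP 6.1.1 repeats this, and no offset or substitution is visible in either place. SAP 6.1.3 gives the distributional assumption, "The natural log transformed inflammatory facial lesion count is expected to be approximately normally distributed", and the reporting rule, "The results of the treatment effects will be presented as geometric means by back-transforming the estimates from the log-scale".

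Zeros are mentioned once, for the descriptive tables in SAP 6.1.2: "A geometric mean will not be reported if the dataset includes zero values".

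On inclusion, SAP 6.1.3.1 says: "All patients with available data after baseline and until Week 12 will be included in the interim and in the primary analyses". It relies on data being missing at random, meaning that "given observed data the missingness does not depend on unobserved data".

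The two success criteria in SAP 6.1.3 are "If there is at least 90% probability that the treatment effect of LYS006 at 12 weeks is better than placebo" and "If there is at least 50% probability that the treatment effect at 12 weeks is at least 25% in favor of LYS006", the second being a difference below -0.288 on the log scale.

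Parts of Protocol 11.4 and 11.4.2 and of SAP 6.1.3 are redacted, as are both sensitivity-analysis sections (Protocol 11.4.4, SAP 6.1.4).

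**The concern.** A patient with no inflammatory lesions at a visit has no defined response there. If software turns log(0) into a missing value, the model treats it as missing at random, yet it is missing because the outcome was the best possible. If such patients are mostly on active drug, the estimated effect shrinks, and the trial could miss its 25% criterion because the drug worked very well in a few people.

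With about 20 completers per arm, one patient is 5% of an arm, so a single zero could matter. The SAP's awareness of zeros in 6.1.2, without a matching rule for the model, makes the omission more noticeable.

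**Working it through.** **Inputs.** From Protocol 11.7: log-normal counts, placebo median 20 at Week 12, true effect 35% (active median 20 × 0.65 = 13), 15 per arm at the interim and 20 per arm at the end, cumulative operating characteristics. From Protocol 4.1: 20 to 100 lesions at baseline, so the log baseline covariate never meets a zero. The visible text gives neither the log SD nor a clearance rate. Both are assumptions below.

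**1. Reproduce Table 11-1.** With flat priors, both criteria hold when the estimate is below -max(1.2816 × SE, 0.288), with SE = SD × √(2/n). Solving the interim 80% for the SD gives 0.465.
- Interim: SE = 0.465 × √(2/15) = 0.170. Success is Φ((0.431 − 0.288)/0.170) = 80%; under no effect, Φ(−0.288/0.170) = 4.5%.
- Cumulative final (correlation √(15/20) between looks): 87.4% and 5.2%.
- The table states 80% and 5%, then 87% and 5%, so it reproduces.

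**2. How likely is a zero?** The chance that a log-normal count rounds to zero is Φ(ln(0.5/median)/SD).
- Placebo: Φ(−3.689/0.465), about 1e-15.
- Active: Φ(−3.258/0.465), about 1e-12.

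Real counts vary more, and 0.465 may be an SD after baseline adjustment, so take log SDs from 0.465 to 1.0. On active, a Poisson-lognormal gives P(zero) of 0.06% to 1.4%, or 20 × 0.0006 = 0.01 to 20 × 0.014 = 0.28 zeros per 20 patients. A negative binomial gives 0.2% to 12%.

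**3. Does handling matter at those rates?** With Poisson-lognormal counts, a 35% effect and the same SD range, dropping zeros and setting them to 0.5 differ by about one percentage point of success at most.

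**4. What if clearance is imposed?** Simulation, assuming SD 0.465, Week 8–Week 12 correlation 0.6, 20 per arm, final look only, lowest counts cleared. Cells show the estimated reduction and the chance of meeting both criteria.

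| True effect; clearance | Zeros dropped | log(count+1) | Zero set to 0.5 |
|---|---|---|---|
| 35%; none | 34.9%, 85% | 33.1%, 81% | 34.9%, 85% |
| 35%; 5% on active only | 32.9%, 78% | 39.0%, 87% | 42.1%, 89% |
| 35%; 15% on active only | 29.1%, 65% | 50.5%, 96% | 55.7%, 97% |
| 35%; 5% in both arms | 35.1%, 86% | 32.0%, 62% | 33.7%, 59% |
| 0; 5% in both arms | 0%, 2% | 0%, 9% | 0%, 10% |

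Dropping lowers the estimate only when clearance is more frequent on active. With equal clearance it is unbiased, and the constants do the damage.

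**5. Understated against what?** With any zero in an arm, its geometric mean is zero, so no true log-scale effect exists to serve as reference. Protocol 11.7 reads the 25% target as a difference in medians. Take a 15% effect in the other patients and 1 of 20 cleared:
- Mean count: 1 − 0.85 × 0.95 = 19.25% reduction, log −0.214.
- Median: (0.5 − 0.05)/0.95 = 0.474, a normal quantile of −0.066. The ratio is 0.85 × exp(−0.066 × 0.465) = 0.824, a 17.6% reduction, log −0.193.
- Zeros dropped: average estimate −0.22, close to both.
- Zero set to 0.5: average estimate −0.335, and 1 − exp(−0.335) = 28.5%, above both.

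In this case the effect is below 25% on the mean and the median. The rise in success from 32% (dropped) to 59% (0.5) therefore consists of extra passes with the target unmet.

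**The case for a change.** The strongest case is that an unwritten choice can decide the result. One zero set to 0.5 against an active median of 13 moves the arm mean by (ln 0.5 − ln 13)/20 = −0.16, more than half of 0.288. If counts are as dispersed as a negative binomial with log SD 1.0, the chance of at least one zero among 20 active patients is 92%. With a 25% effect in the others and one patient cleared on active only, success is 66% with zeros dropped against 86% with 0.5. There the mean reduction is 1 − 0.75 × 0.95 = 28.75%, so that loss would be genuine. The supportive change-from-baseline models in SAP 6.1.5 keep zeros but attach only the probability of any benefit, not the 25% criterion. The redactions give limited comfort, since the visible endpoint definitions read as complete.

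What stands is that no rule is visible and that handling would matter if zeros were common or lopsided. The rest is conditional. The 92% comes from the far end of an assumed range, and at 0.465 the same model gives 4%. Clearance confined to active is imposed, not taken from the documents. Nor is a substituted constant a safe remedy: with one patient cleared on active and no effect in the other 19, one simulation put success at 8% with the zero dropped and 22% with 0.5. Using log(count+1) also shifts the target, since a fall from 20 to 15 lesions becomes ln(16/21) = −0.272.

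**Conclusion.** The omission is real but is a missing convention, not an error in the analysis. Nothing in the plan discards zeros. If log(0) did become missing, the patient's other visits would stay in the repeated-measures model. Under the plan's own distribution a Week 12 zero is practically impossible. With Poisson variation and log SDs of 0.465 to 1.0, the choice between dropping and 0.5 is worth about one percentage point of success.

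Larger shifts need clearance rates the documents do not support, and they run either way: 85% falls to 65% if zeros are dropped with 15% clearing on active only, while 86% with zeros dropped becomes 59% with 0.5 when 5% clear in both arms. No constant is clearly better, so prescribing one exchanges one conditional bias for another.

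An analyst meeting a zero would have to adopt a convention, and its influence could be seen: SAP 6.1.2 lists every count by group, patient and visit, and SAP 6.1.5 analyses absolute and percentage change without logs. The study is a non-confirmatory proof of concept whose criteria guide a decision that may weigh other evidence. The conclusion rests on the back-solved SD and on zeros being rare. A redacted rule is possible, but the conclusion does not depend on it.
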